4.6.2. Adverse Events

4.6.2.1. Treatment Emergent Adverse Events

A TEAE for the double-blind treatment period is defined as an event that first occurred or worsened in severity after the randomization to the double-blind treatment period. The definition of baseline and postbaseline for double-blind treatment period are specified in [Table GPHN.4.1](#). The MedDRA LLT will be used in the treatment-emergent derivation. The maximum severity for each LLT during the baseline period including ongoing medical history will be used as baseline severity. For events with a missing severity during the baseline period, it will be treated as “mild” in severity for determining treatment-emergence. Events with a missing severity during the postbaseline period will be treated as “severe” and treatment-emergence will be determined by comparing to baseline severity.

The counts and percentages of randomized participants with TEAEs will be summarized by treatment using MedDRA PT nested within SOC. Statistical comparisons will be applied at both the SOC and PT levels. Events will be ordered by decreasing frequency within SOC. The SOC will be in alphabetical order. For events that are sex-specific, the denominator and computation of the percentage will include only participants from the given sex.

An overview of the number and percentage of participants who experienced a TEAE, SAE, death, discontinued from study treatment or study due to an AE, relationship to study drug will be summarized for all randomized participants by treatment.

The counts and percentages of randomized participants with TEAEs by maximum severity will be summarized by treatment using MedDRA PT. For each participant and TEAE, the maximum severity for the MedDRA PT is the maximum postbaseline severity observed from all associated LLTs mapping to the MedDRA PT. The maximum severity will be determined based on the nonmissing severities. If all severities are missing for the defined postbaseline period of interest, it will show as missing in the table.

4.6.2.2. Common Adverse Events

The counts and percentages of randomized participants with TEAEs, overall and common (common TEAEs occurred in $\geq 5\%$ of participants in any treatment group before rounding), will be summarized by treatment using MedDRA PT. Events will be ordered by decreasing frequency.

4.6.3. Additional Safety Assessments

4.6.3.1. Deaths

Listing of all deaths will be provided by study period. The listing will include participant identification including the treatment, site number, date of death, age at the time of enrollment, sex, associated AE group identification, time from last dose of study drug to death (if participant had discontinued study drug), and primary cause of death.

Additional deaths that are reported outside of the study period will be obtained from the Lilly Safety System (LSS), which will be provided by Global Patient Safety.

4.6.3.2. Other Serious Adverse Events

The counts and percentages of randomized participants who experienced at least 1 SAE (including deaths and SAEs temporally associated with or preceding deaths) during the postbaseline period will be summarized by treatment using MedDRA PT nested within SOC. Events will be ordered by decreasing frequency within SOC. The SOC will be in alphabetical order.

A listing of all SAEs will be provided. The listing will include (not limited to) treatment, participant identification including the site number, participant number, date of event, age at the time of enrollment, sex, MedDRA SOC and PT, reported term, severity, outcome, relationship to study drug, time from first dose of study drug to the event, AE start date, AE end date, and action taken related to study treatment.

4.6.3.3. Other Significant Adverse Events

The counts and percentages of participants who discontinued from study treatment or study due to an AE during the double-blind treatment period may be summarized by treatment group using MedDRA PT nested within SOC. Events will be ordered by decreasing frequency within SOC.

In addition, for patients randomized to the Tirzepatide treatment group during the double-blind treatment period, the following analyses will be conducted, note that baseline for analyses listed below is the same as the safety outcome baseline defined in open label period [Table GPHN.6.1](#):

- counts and percentages of participants who had resting pulse increases from baseline at 2 or more consecutive visits of more than 10 bpm and/or 20 bpm
- counts and percentages of participants who had resting pulse at any postbaseline visit increases from maximum baseline ≥20 bpm

In addition, the following analyses will be conducted by treatment group during the double-blind treatment period:

- counts and percentages of participants who had at least 1 resting pulse at any postbaseline visit exceeding 100 bpm
- counts and percentages of participants who had at least 1 resting pulse exceeding 100 bpm occurring at 2 or more consecutive study visits

4.6.3.5. Electrocardiograms

Summary statistics by treatment and by nominal visit will be provided for electrocardiogram (ECG) parameters (heart rate, PR interval, QRS, QT, and Fridericia's corrected QT interval (QTcF) [$QTcF = QT/RR^{0.333}$]). When the QRS is prolonged (eg, a complete bundle branch block), QT and corrected QT (QTc) should not be used to assess ventricular repolarization. Thus, for the analysis purposes, the QT and QTcF value will be set to missing when QRS is ≥120 msec for a particular ECG.

Change from baseline to postbaseline values for ECG parameters (heart rate and PR interval) will be summarized for participants who have both a baseline and at least 1 postbaseline result. Only scheduled measurements will be included in the mean change analyses.

The counts and percentages of participants who meet the following criteria at any time during the double-blind treatment period (including the safety follow up time period) will be summarized by treatment group:

- QT >500 msec
- QTcF >500 msec
- QTcF >480 msec

For patients randomized to Tirzepatide treatment group, the counts and percentages of participants who meet the following treatment-emergent criteria during the double-blind

treatment period (including the safety follow up time period) will be summarized. The baseline for treatment emergent abnormal ECG parameters is the same as the safety outcome baseline defined in open label period ([Table GPHN.6.1](#)):

- Treatment-emergent ECG abnormalities as listed in [Table GPHN.4.6](#).
- Treatment-emergent increase from the maximum baseline in QTcF interval of >30 msec, 60 msec, or 75 msec. Maximum baseline (see [Table GPHN.4.1](#) for details) will be the maximum non-missing observation in the baseline period. The maximum value during the double-blind treatment period will be analyzed. Scheduled and unscheduled measurements will be included.

Table GPHN.4.6. Selected Categorical Limits for ECG Data

Parameter	Low		High	
	Males	Females	Males	Females
Heart Rate (bpm)	<50 and decrease ≥15	<50 and decrease ≥15	>100 and increase ≥15	>100 and increase ≥15
PR Interval (msec)	<120	<120	≥220	≥220
QRS Interval (msec)	<60	<60	≥120	≥120
QTcF (msec)	<330	<340	>450	>470

Abbreviations: bpm = beats per minute; ECG = electrocardiogram; QTcF = Fridericia's corrected QT interval.

4.6.3.6. Clinical Laboratory Evaluation

Descriptive summaries at each planned visit by treatment group will be provided for the baseline and postbaseline values and change from baseline values. The associated descriptive summaries will be presented in SI units and in CN units. Limits from the performing laboratory will be used to define low and high.

Observed and change from baseline to each visit will be displayed for participants who have both a baseline and at least 1 postbaseline planned measurement. Baseline is defined in [Table GPHN.4.1](#).

A shift table will be provided including unscheduled measurements. The shift table will include the number and percentage of participants within each baseline category (low, normal, high, or missing) versus each postbaseline category (low, normal, high, or missing) by treatment. The proportion of participants shifted will be compared between treatments using Fisher's exact test.

For qualitative laboratory analytes, the number and percentage of participants with normal and abnormal values will be summarized by treatment.

A listing of abnormal findings will be created for laboratory analyte measurements, including qualitative measures. The listing will include participant identification, treatment group, laboratory collection date, study day, analyte name, and analyte finding.

The MMRM model or ANCOVA (if MMRM model is not applicable) will be used for the analysis during the double-blind treatment period for the continuous measurements for selected lab tests.

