##### ***9.4.4.4.4. Central Laboratory Measures, Vital signs, and Electrocardiograms***

Actual values and change from randomization of central laboratory measures, vital signs, and selected ECG parameters will be summarized by treatment group at each scheduled visit.

The percentages of participants with treatment-emergent abnormal, high, or low measures (including lab, vital, and ECG parameters) at any time will be summarized and compared between treatment groups using Fisher's exact test.

The analysis details will be provided in the SAP.

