Unless specified otherwise, for analyses in the double-blind treatment period, baseline is defined as the last nonmissing data collected prior to or at randomization (Week 36); for analyses including data collected in open-label lead-in period, baseline is defined as the last nonmissing data collected prior to or at study enrollment (Week 0).

For some specific safety related parameters, the definition of baseline and postbaseline for double-blind treatment period are specified in [Table GPHN.4.1](#).

The definition of baseline and postbaseline during the open-label lead-in treatment period can be found in [Appendix 4](#).

Table GPHN.4.1. Baseline and Postbaseline Definitions for Safety Outcomes in Double-Blind treatment Period

Analysis Set	Analysis Type	Baseline	Postbaseline
SS	1.1) Treatment-Emergent Adverse Events	Ongoing at the time of the randomization to the double-blind treatment period.	Starts after randomization visit and ends after the whole study period (including off-drug follow-up visit).
SS	1.2) Treatment-Emergent Abnormal Labs ^a , Vital Signs, and ECGs.	Refer to Table GPHN.6.1 for baseline definition.	Postbaseline will be defined as above (1.1). All scheduled and unscheduled measurements will be included.
SS	1.4) Change from Last Baseline to Week xx and to Last Postbaseline for Labs ^a , Vital Signs, and ECGs.	The last scheduled and unscheduled non-missing assessment recorded during the open-label lead-in period.	Postbaseline will be defined as above (1.1). Only scheduled visits will be included. The ED visits are considered scheduled visits.

Abbreviations: ECGs = electrocardiogram; ED = early discontinuation; SS = Safety Analysis Set.

^a Immunogenicity-related analysis is specified in Section [4.6.5.5](#).

For the primary and key secondary efficacy endpoint analyses subject to type 1 error rate control, data for participants with missing values at the 88-week visit (or weight-related measurements at 64-week visit) will be imputed based on the method described in Section [4.3.2.3](#). Otherwise, missing values will not be explicitly imputed except for the parameters with only 1 postbaseline measure during the analysis period per schedule of activity, where LOCF approach will be applied to impute the endpoint when ED measure is available.

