Compare tirzepatide MTD QW with placebo from randomization to Week 88	
 • SF-36v2 acute form Bodily Pain domain (BP) • SF-36v2 acute form General Health domain (GH) • SF-36v2 acute form Vitality domain • SF-36v2 acute form Social Functioning domain (SF) • SF-36v2 acute form Physical-Component Summary score • SF-36v2 acute form Mental-Component Summary score • IWQOL-Lite-CT total score • IWQOL-Lite-CT Physical composite score • IWQOL-Lite-CT Psychosocial composite score • EQ-5D-5L utility score • EQ-5D-5L VAS score 	Data from randomization to Week 88 will be included. ANCOVA model with terms of treatment (tirzepatide MTD, placebo), all stratification factors, and corresponding score at randomization at Week 36 as a covariate. Missing data will be imputed using LOCF.

Abbreviations: ANCOVA = analysis of covariance; BMI = body mass index; HDL = high-density lipoprotein; IWQOL-Lite-CT = Impact of Weight on Quality of Life-Lite-Clinical Trials Version; LDL = low-density lipoprotein; MTD = maximum tolerated dose; QW = once weekly; SF-36 v2 acute form = Short Form-36 Version 2 Health Survey acute form; VAS = visual analog scale; VLDL = very low-density lipoprotein.

4.6. (Other) Safety Analyses

Unless specified otherwise, safety assessments for the double-blind treatment period will be based on the SS ([Table GPHN.3.1](#)). All data collected between randomization and the end date of study participation will be included, regardless of the adherence to study intervention.

Safety outcomes during the open-label lead-in treatment period will also be summarized for all enrolled participants. Detailed analyses can be found in [Appendix 3](#).

The statistical assessment of homogeneity of the distribution of categorical safety responses between tirzepatide MTD and placebo will be conducted using Fisher's exact test, unless specified otherwise.

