The mean change from baseline differences among treatments at all scheduled visits will be assessed via an MMRM using REML. Unless specified otherwise, if the safety parameter is assessed at 88 weeks, then the model will include country/pooled country, sex, tirzepatide MTD dose at randomization, percent weight loss at randomization (<10% and $\geq 10\%$), treatment group, visit and treatment-by-visit interaction as fixed effects, and baseline value of the safety parameter as a covariate. To model the covariance structure within participants, the unstructured covariance matrix will be used. If this model fails to converge, the covariance structures specified in

Section 4.3.2.2 will be tested in order until convergence is met. If the data does not warrant the MMRM model, then ANCOVA model will be conducted.

For selected parameters, time-to-first-event analysis via the Cox-proportional hazards model may be conducted. Participants without the event will be censored at the end of study participation.

For participants experiencing the event, the “time-to-first-event” will be the time (in weeks) from first dose or randomization (depends on the event of interest and analysis feature, eg, for time to study discontinuation, time from first dose might be used; for time to AE during double-blind treatment period, time from randomization might be used) to first occurrence of the event.

Where necessary, the rate of events will be analyzed using a generalized linear mixed-effects model assuming the number of events follows a negative binomial distribution and with treatment as a fixed effect. The logarithm of days during the double-blind treatment period will be adjusted as an offset to account for possible unequal treatment duration of follow-up between participants.

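### The only categorical between-arm lab test in SAP 4.6.3.6 is on an undefined proportion shifted, and the protocol's directional comparison of treatment-emergent abnormal labs is not carried over

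*SAP*

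**What the plan says.** Protocol 9.4.4.4.4 sets the question in directional terms. Its subject is: "The percentages of participants with treatment-emergent abnormal, high, or low measures (including lab, vital, and ECG parameters) at any time". The two arms are to be contrasted on these with Fisher's exact test. The protocol leaves the details to the SAP.

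SAP 4.6.3.6 does not take this up. It plans a shift table of "each baseline category (low, normal, high, or missing) versus each postbaseline category (low, normal, high, or missing) by treatment", including unscheduled measurements, and then states: "The proportion of participants shifted will be compared between treatments using Fisher's exact test". It does not say which moves count as a shift or how the missing category is treated. It also does not say whether the maximum, minimum or last postbaseline value is classified.

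For baseline, the section refers to Table GPHN.4.1. That table has two candidate rows:

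- Row 1.2, labelled "1.2) Treatment-Emergent Abnormal Labs" (with vital signs and ECGs), points to Table GPHN.6.1, where the baseline period ends before the first dose.
- Row 1.4, for change from last baseline, uses the last assessment in the open-label lead-in, when everyone is on tirzepatide.

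Protocol 9.4.1 asks that changes of analysis method, with their justification, be described in the SAP and the study report. SAP 4.9 lists only the promotion of two weight-loss responder endpoints.

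**The concern.** The protocol asks whether more participants on one arm become abnormal. A test on any change of category asks something else. Normal to high, high to normal, normal to low and low to normal all count as the same event, and moves to or from missing may count too. The null becomes equal chance of changing category.

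The design makes this matter. All participants are on drug at randomisation and half are then switched to placebo. If the drug pushes an analyte out of range, new abnormal values can appear on tirzepatide while existing ones resolve on placebo. If weight regain drives the analyte, the pattern runs the other way. In both cases opposite movements enter the same numerator.

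A non-significant result could then sit on top of a real excess of new abnormal values, and a significant one could reflect normalisation alone. The analytes most exposed are those with no other categorical display: haematology, electrolytes, bicarbonate, calcium, uric acid, albumin and creatine kinase.

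**Working it through.** **Inputs.** From the documents: 300 per arm (Protocol 9.2, SAP 5), Fisher's exact test, 2-sided alpha 0.05. The documents give no laboratory shift rates and no power for any lab test, so there is no planned figure to reproduce here. Their only power statement, above 90% for the primary endpoint, is met and is not in question. All rates below are assumptions.

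**Set-up.** Let b be the proportion high at baseline, n the rate of new highs among those normal at baseline, and r the rate of resolution among those high at baseline. With low values ignored for simplicity, the proportion shifted in any direction in an arm is

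s = (1 − b) × n + b × r.

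The directional test compares n between arms among participants normal at baseline. The pooled test compares s over all 300 per arm. Pooled power is by exact enumeration. Directional power is by simulation, with the number normal at baseline drawn at random.

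**Loss of power.** New highs are 10% on tirzepatide and 3% on placebo. Worked example with b = 25% and resolution 15% versus 40%:

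- tirzepatide: 0.75 × 0.10 + 0.25 × 0.15 = 0.0750 + 0.0375 = 11.25%
- placebo: 0.75 × 0.03 + 0.25 × 0.40 = 0.0225 + 0.1000 = 12.25%

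A 7-point excess of new highs has become a 1-point difference in the opposite direction.

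| High at baseline | Resolution, tirzepatide vs placebo | Shifted, tirzepatide vs placebo | Directional power | Pooled power |
|---|---|---|---|---|
| 25% | 15% vs 40% | 11.25% vs 12.25% | about 85% | about 5% |
| 10% | 15% vs 40% | 10.5% vs 6.7% | about 91% | about 33% |
| 5% | 15% vs 40% | 10.25% vs 4.85% | about 93% | about 66% |
| 25% | 30% vs 30% | 15.0% vs 9.75% | about 85% | about 45% |
| 10% | 30% vs 30% | 12.0% vs 5.7% | about 91% | about 74% |
| 5% | 30% vs 30% | 11.0% vs 4.35% | about 93% | about 84% |

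If exactly 225 per arm are normal at baseline, exact enumeration gives 83.4% for the directional test, close to the simulated 85%.

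The equal-resolution rows show that opposing movement is not needed for a loss. Resolution adds the same amount to both arms, so it adds noise without adding signal.

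**Rejection on normalisation alone.** Set new highs at 5% in both arms, so the protocol's null is true. With b = 25% and resolution 15% versus 40%, s is 0.0375 + 0.0375 = 7.5% versus 0.0375 + 0.1000 = 13.75%. The pooled test rejects about 66% of the time. With resolution 50% versus 20%, s is 16.25% versus 8.75% and it rejects about 77%. At b = 10% and 5%, with 15% versus 40%, rejection falls to about 17% and 7%. The directional test stays near 4% throughout.

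**Bounds, with rates as shares of all 300 per arm.** New abnormality 10% versus 3% and normalisation 3% versus 10% give 13% versus 13% shifted: pooled power 3.8%, directional 92.9%. With no normalisation in either arm, both tests have 92.9%. If normalisations also favour tirzepatide (10% versus 3%), the pooled test reaches 99.9%, but it is then partly detecting normalisation.

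**Baseline.** These scenarios need participants who are abnormal at baseline. With row 1.4, abnormalities induced during the lead-in are in the baseline and can resolve on placebo, so the opposing pattern is natural. With row 1.2, such abnormalities are not yet present at baseline. Their later resolution is then normal to normal, and cancellation is weaker. Differential normalisation of values that were abnormal before treatment can still drive the test.

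Moves to or from missing are not modelled.

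**The case against.** A reader might infer that this is the only between-arm lab test, so that a drug-related lab harm could go unseen. The documents do not support that. SAP 4.6 says "The mean change from baseline differences among treatments at all scheduled visits will be assessed via an MMRM using REML", and SAP 4.6.3.6 adds for selected labs: "The MMRM model or ANCOVA (if MMRM model is not applicable) will be used for the analysis during the double-blind treatment period". Both keep the sign of the change.

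Other protection also remains:

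- Every shift cell is shown by arm, and abnormal findings are listed with treatment group.
- Protocol 8.2.4 has clinically relevant lab changes reported as adverse events, and SAP 4.6.2.1 compares treatment-emergent events between arms.
- Liver enzymes, pancreatic enzymes and calcitonin have threshold summaries; eGFR and UACR have directional shift tables.
- Safety tests are unadjusted, and no decision rule rests on this one.

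It can also be said that counting any direction is a reading of an undefined term, since the SAP never states it. The same holds for counting missing. And because the shift table includes unscheduled measurements, it matches row 1.2 better than row 1.4, which would put baseline before the first dose and weaken the withdrawal mechanism. Finally, the most severe figures need a high baseline prevalence with opposing resolution, and no rates for the exposed analytes are given.

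All of this limits the concern, but it does not remove it. A mean-change model does not answer how many participants became abnormal. The protocol's own comparison is no safeguard if the SAP does not carry it out. An undefined event and an open baseline are themselves defects in a prespecified test.

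**Conclusion.** The concern holds for the categorical test. SAP 4.6.3.6 tests an undirected proportion with an open baseline and an untreated missing category. It drops the directional comparison in Protocol 9.4.4.4.4, although Table GPHN.4.1 still defines a baseline for it, and SAP 4.9 does not record the departure.

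Read literally, the test can lose power for new abnormalities or reject on normalisation alone. With 25% high at baseline and new highs of 10% versus 3%, power falls from about 85% to 45% (equal 30% resolution) or about 5% (15% versus 40%). At 5% high at baseline it falls from about 93% to 84% or 66%. All these rates are assumed, with 300 evaluable per arm. Full cancellation after withdrawal applies mainly with an end-of-lead-in baseline, which the SAP does not fix.

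The inference that a lab harm would pass unnoticed goes too far, given the mean-change models and by-arm displays.

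**What to change.** In SAP 4.6.3.6, replace the sentence on the proportion shifted with two Fisher comparisons per analyte, among participants with a nonmissing baseline and at least one postbaseline value:

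- **Treatment-emergent high:** not high at baseline, maximum postbaseline value high.
- **Treatment-emergent low:** not low at baseline, minimum postbaseline value low.

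Do not count missing as a shift. Keep the 4 × 4 table as a descriptive display without a p-value.

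State which Table GPHN.4.1 baseline applies. If the value at randomisation is used for the between-arm test, record that as a change from row 1.2. Protocol 9.4.4.4.4 gives no maximum/minimum rule and no denominator, so these are details the SAP supplies. List any remaining departure from that section in SAP 4.9.

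The cost is SAP wording and standard table programming, with no new data. The small downside is two unadjusted safety tests per analyte instead of one.
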